1.3 Schedule of Activities

[Table 1](#) summarizes the SoA for the screening and treatment period for Arm A (AZD7442 Q3M).

[Table 2](#) summarizes the SoA for the screening and treatment period for Arm B (AZD7442 Q6M).

[Table 3](#) summarizes the SoA for the follow-up period for Arm A and Arm B.

[Table 4](#) summarizes the assessments to be conducted when Illness Visits are initiated for participants who are suspected to have COVID-19.

Participants who permanently discontinue IMP administration due to the premature termination of the study will remain in the study to complete visits/assessments (except those related to monitoring of IMP administration) for at least 6 months after their final dose of AZD7442.

- If participants receive their last study drug administration on Day 183 visit, they will complete Day 190, Day 212, and Day 274 (no dosing) visits, followed by an Early Discontinuation visit in place of the Day 365 visit.
- If participants receive their last study drug administration on Day 274 visit, they will complete Day 281, and Day 365 (no dosing) visits, followed by an Early Discontinuation visit in place of the Day 456 visit.
- If participants have already completed visit/assessments up to 6 months after the last IMP administration (i.e. Day 365), the early discontinuation visit will be scheduled as early as possible. However, if early discontinuation scheduling is within one month of last completed in person visit and required samples were collected per protocol, then no additional sample collection is required (with the exception of a urine pregnancy test for WOCBP, and if positive or indeterminant, serum pregnancy will be collected).
- If participants are completing an illness visit series, they will be followed until completion or until the Early Discontinuation visit.

Table 1 Schedule of Activities: Treatment Period – Arm A (AZD7442 Q3M)

Period	Screen ^a	Treatment (Days 1-456)													EoT	For details, see Section
Day (* = IMP dosing day)	-7 to 1	1*	8	29	92*	99	121	183*	190	212	274*	281	365*	372	456	
Week (Month)	-	-	1	4	13 (3M)	14	17 (4M)	26 (6M)	27	30 (7M)	39 (9M)	40	52 (12M)	53	65 (15M)	
Window (days)	-	-	± 3	± 5	± 7	± 3	± 5	± 7	± 3	± 5	± 7	± 3	± 7	± 3	± 15	
P = In-Person Visit RTM = Remote TM Visit ^m	P	P	RTM/ P ^m	P	P	RTM/ P ^m	P	P	RTM/ P ^m	P	P	RTM/ P ^m	P	RTM/ P ^m	P	
Procedure																
Informed consent	X															5.1
Informed assent for pediatric participants	X															5.1

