Week (Month)	-	-	1	4	13 (3M)	26 (6M)	27	30 (7M)	39 (9M)	52 (12M)	53	65 (15M)	
Window (days)	-	-	± 3	± 5	± 7	± 7	± 3	± 5	± 7	± 7	± 3	± 15	
P = In-Person Visit RTM = Remote TM Visit ⁿ	P	P	RTM/ P ⁿ	P	P	P	RTM/ P ⁿ	P	P	P	RTM/ P ⁿ	P	
Nasopharyngeal samples													
Documented negative SARS-CoV-2 RT-PCR test from NP specimen taken ≤ 3 days before Day 1 ^d OR SARS-CoV-2 rapid antigen test	X ^e												8.2.4
SARS-CoV-2 RT-PCR (central laboratory) (predose)		X ^f											8.2.4
Urine samples													
Pregnancy test – urine (WOCBP only) ^g ; (predose on days of IMP administration)	X	X ^h		X	X	X		X	X	X		X	5.3, 8.2.4, 8.3.9.1
Urinalysis (predose on days of IMP administration)		X			X	X			X	X		X	8.2.4
PK, PD, ADA assessments													
Serum sample for AZD7442 PK assessment (predose on days of IMP administration unless otherwise noted)		D1 ⁱ , D3 (±1d)) ^j	D11 (±3d) ^k	X	X	X		X	X	X		X	8.5.1
Serum sample for AZD7442 ADA assessment (predose on days of IMP administration)		X		X	X	X		X	X	X		X	8.5.2.1
Serum sample for SARS-CoV-2 nAbs assessment (predose on days of IMP administration)		X		X	X	X		X	X	X		X	8.5.3.1

Table 2 Schedule of Activities: Treatment Period – Arm B (AZD7442 Q6M)

Period	Screen ^a	Treatment (Days 1-456)										EoT	For details, see Section
Day (* = IMP dosing day)	-7 to 1	1*	8	29	92	183*	190	D212	274	365*	372	456	
Week (Month)	-	-	1	4	13 (3M)	26 (6M)	27	30 (7M)	39 (9M)	52 (12M)	53	65 (15M)	
Window (days)	-	-	± 3	± 5	± 7	± 7	± 3	± 5	± 7	± 7	± 3	± 15	
P = In-Person Visit RTM = Remote TM Visit ⁿ	P	P	RTM/ P ⁿ	P	P	P	RTM/ P ⁿ	P	P	P	RTM/ P ⁿ	P	
NLF sample for mucosal response assessments ^l (predose on days of IMP administration unless otherwise noted)		D1 ⁱ , D3 (±1d)) ^j	D11 (±3d) ^k	X	X	X		X	X	X		X	8.5.2.3
Serum sample for SARS-CoV-2 serology (anti-nucleocapsid) testing (predose on days of IMP administration)		X		X	X	X		X	X	X		X	8.5.2.2
IMP Administration													
Arm B: AZD7442 administration		X				X				X			6.1, 6.2
Postdose safety monitoring ^m		X	X			X	X			X	X		8.2.5
Safety assessments													
AEs/SAEs/AESIs	SAEs only	←-----→										8.3	
Monthly contact between visits													
Monthly telephone/email/text contacts - monitoring for COVID-19 symptoms and safety ^p													8.1.1, 8.3

^a Screening activities may be collected over more than one visit if necessary; if screening and dosing occur at the same visit, only one evaluation is required, unless otherwise specified.

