Serum sample for SARS-CoV-2 nAbs assessment				X	8.5.3.1
NLF sample for mucosal response assessments ^d				X	8.5.2.3

Table 3 Schedule of Activities: Follow-up Period (Arm A and Arm B)

Period	Follow-up (Days 457-729)			Early Discontinuation ^a	For details, see Section
	Day	638	729		
Week (Month)	78 (18M)	91 (21M)	104 (24M)		
Window (days)	± 15	± 15	± 15		
P = In-Person Visit RTM = Remote TM Visit	RTM/ Telephone call	RTM/ Telephone call^b	P	P	
Serum sample for SARS-CoV-2 serology (anti-nucleocapsid) testing				X	8.5.2.2
Safety assessments					
AEs/SAEs/AESIs	X	X	X	X	8.3
Monthly contact between visits					
Monthly telephone/email/text contacts - monitoring for COVID-19 symptoms and safety ^f	←----->				8.1.1, 8.3

^a The Early Discontinuation Visit is only applicable for participants who withdraw from the study and for premature termination of the study. See Section 7.2. and Section 7.4.

^b If local facilities or local regulations do not allow for an RTM visit, contact with participants should be made by telephone.

^c If the urine pregnancy test is positive or indeterminate, a quantitative serum β-hCG will be performed by the central laboratory for confirmation.

^d When test supplies are available, sampling should be performed.

^e Targeted physical examination per investigator discretion will include areas suggested by medical history, vulnerable conditions and reported clinical complaints during the study visit and may require height and weight.

^f Monthly contact with participants to remind them to present to the study site for SARS-CoV-2 testing if they have qualifying symptoms. The Investigator will enquire about any COVID-19 symptoms from previous 30 days and other adverse events.

ADA, antidrug antibody; AE, adverse event; AESI, adverse event of special interest; β-hCG, beta-human chorionic gonadotropin; ECG, electrocardiogram; FSH, follicle-stimulating hormone; M, month; nAb, neutralizing antibody; NLF, nasal lining fluid; PK, pharmacokinetics; PD, pharmacodynamics; SAE, serious adverse event; SARS-CoV-2, severe acute respiratory syndrome-coronavirus-2; TM, telemedicine; WOCBP, women of childbearing potential.

Table 4 Schedule of Activities: Illness Visits (Participants with COVID-19 Clinical Symptoms)

Procedure	Site Visit		Site Visit for SARS-CoV-2 positive participants only ^{a, b}					Long COVID-19 monitoring	For details, see Section
	Day ^c	IL-D1a	IL-D1b ^d	IL-D5	IL-D7	IL-D14	IL-D28	IL-D90	
Window (days)	NA	NA	± 2	± 2	± 2		± 7	± 7	

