3.3.2 Visit Window

A windowing convention will be used to determine the analysis value for a given study visit for visit-based assessments, which are as follows:

- Serum sample for SARS-CoV-2 serology (anti-nucleocapsid testing)
- Serum sample for AZD7442 PK assessments
- Serum sample for AZD7442 ADA
- Serum sample for SARS-CoV-2 nAbs levels (pharmacodynamics [PD])
- Serum sample exploratory biomarkers
- Nasal lining fluid sample for AZD7442 PK assessments
- Clinical chemistry, hematology, coagulation, and urinalysis
- Vital signs
- Electrocardiogram (ECG)
- Illness visits for COVID-19 symptom assessment, vital signs, immunogenicity, PD, PK, coagulation, serum sample for exploratory assessments

The window for the visits following baseline will be constructed in such a way that the upper limit of the interval falls halfway between the two visits (the lower limit of the first post-baseline visit will be Day 2). If an odd number of days exists between two consecutive visits, then the upper limit will be taken as the midpoint value minus 1 day.

One or more results for a particular variable may be obtained in the same visit window. In such an event, the result with the date closest to the expected visit date will be used in the analysis. In the event that two observations are equidistant from the expected visit date, the later observation will be used in the analysis.

The visit windows are defined in the following tables.

Table 3: Analysis windows for serum sample for SARS-CoV-2 serology, ADA and SARS-CoV-2 nAbs levels

Arm A

Visit	Day Relative to First Dose	Visit Window (Study Day)
Day 1	≤ 1	≤ 1
Day 29	29	2 – 60
Day 92	92	61 - 106
Day 121	121	107 - 152
Day 183	183	153 - 197
Day 212	212	198 - 242
Day 274	274	243 - 319
Day 365	365	320 - 410
Day 456	456	≥411 [for serology and SARS-CoV-2 nAbs] 411 – 592 [for ADA assessment]
Day 729 (Follow-up)	729	≥593 [for ADA assessment]

Arm B

Visit	Day Relative to First Dose	Visit Window (Study Day)
Day 1	≤ 1	≤ 1
Day 29	29	2 – 60
Day 92	92	61 - 137
Day 183	183	138 - 197
Day 212	212	198 - 242
Day 274	274	243 - 319
Day 365	365	320 - 410
Day 456	456	≥411 [for serology and SARS-CoV-2 nAbs] 411 – 592 [for ADA assessment]
Day 729 (Follow-up)	729	≥593 [for ADA assessment]

Table 4: Analysis windows for serum sample for AZD7442 PK assessment, NLF sample for mucosal response

Arm A

Visit	Day Relative to First Dose	Visit Window (Study Day)
Day 3	3	2 – 6 [subset of 20 participants, PK and NLF assessment]

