4.2.3.4 Analysis of Exploratory Endpoints

4.2.3.4.1 SARS-CoV-2 RT-PCR-positive Symptomatic Illness

The incidence of SARS-CoV-2 RT-PCR-positive symptomatic illness will be summarized with descriptive statistics in the FAS at the final data readout only. The number and percentage of participants who have the events will be provided overall and before Day 183, or Day 365.

Participants will be included as an event if they have RT-PCR-confirmed SARS-CoV-2 prior to Day 183, or Day 365, after first IMP dose and present with at least one of the qualifying symptoms as defined in the CSP. A positive SARS-CoV-2 RT-PCR will be defined based on the central laboratory result whenever both central and local laboratory results are available for NP swabs, or if only a central lab NP swab result is available. If only a local NP swab laboratory result is available, then the local laboratory result will be used. If no SARS-CoV-2 RT-PCR results are available, the participant will be considered as not having a RT-PCR-positive symptomatic event. Data from the eCRF will be used to determine if the participant met the qualifying symptoms. If a participant's first case of SARS-CoV-2 RT-PCR positive symptomatic illness occurs on or after Day 183, or Day 365, the participant will be considered as not having an event, respectively. Death due to COVID-19 or hospitalization due to COVID-19 can contribute to this endpoint when a qualifying symptom assessment is not observed.

- For participants with an event after first IMP dose, before Day 183, or Day 365, the date of event will be defined as the earliest symptom onset date from those which triggered an illness visit, where COVID-19 was confirmed with a positive SARS-CoV-2 RT-PCR laboratory test. In the case of death due to COVID-19 or hospitalization due to COVID-19, the date of event is the earliest date of death/date of hospital admission when a qualifying symptom is not observed.

If any of the following censoring reasons are met, the censoring date will be defined as follows:

- Participants who had SARS-CoV-2 RT-PCR positive test prior to first IMP dose will be censored at date of first IMP dose.
- Participants who receive a COVID-19 vaccination after first IMP dose, and prior to having an event before Day 183, or Day 365 will be censored at the date of vaccination.

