- Participants who have a protocol deviation for receiving restricted medication after first IMP dose, and prior to having an event before Day 183, or Day 365 will be censored at the date of the deviation.
- Participants who have a record-level exclusionary protocol deviation for PK samples (see Table 5 in most recent version of PDMP) after first IMP dose, and prior to having an event before Day 183, or Day 365 will be censored at the date of the deviation.
- Participants who discontinue early from the study after first IMP dose, and prior to having an event before Day 183, or Day 365 will be censored at date of end of study or date of last assessment, whichever is later. For participants who continue to participate in the study at the time of the analysis, the data cut off (DCO) date will be used as their last assessment date. For participants with no post-baseline visit data available, the date of the first IMP administration will be used i.e., follow-up will be 1 day.

The follow up time will be calculated as the minimum of the date of censoring, date of event, and date of Day 183 or Day 365 – date of first IMP dose + 1. When the minimum of the date of censoring and date of Day 183 or Day 365 is prior to date of event, then participants will be censored at their defined end of follow up time. Otherwise, participants will be identified as having an event at this time.

Time to the first SARS-CoV-2 RT-PCR-positive symptomatic illness episode will be analyzed using Kaplan-Meier (KM) method and quartiles will be presented. Proportion of participants who experience event, participants who are censored, breakdown of events, and reasons for censoring will be presented by treatment group at Day 183 or Day 365. KM plot will also be generated by treatment groups.

A listing will be provided for all COVID-19 symptom assessments and NP swabs assessed by RT-PCR (both local laboratory and central laboratory samples) regardless of RT-PCR result.

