4.2.3.4.2 Post-treatment Response for SARS-CoV-2 Nucleocapsid Antibodies

The incidence of participants who have a post-treatment response (negative at baseline to positive at any time post-baseline) for SARS-CoV-2 nucleocapsid antibodies will be summarized using FAS by treatment group overall and before Day 183, or Day 365 at the final data readout only. Same censoring criteria as described in Section 4.2.3.4.1 will be applied.

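### The Day 183 and Day 365 cut-offs for nucleocapsid seroconversion fall on scheduled blood-draw days, so on-time and late samples drop out, and at Day 183 the two arms lose unequal observation time

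*SAP*

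**What the plan says.** SAP 4.2.3.4.2 reports the proportion of participants who go from nucleocapsid-negative at baseline to positive afterwards, "summarized using FAS by treatment group overall and before Day 183, or Day 365 at the final data readout only". It adds: "Same censoring criteria as described in Section 4.2.3.4.1 will be applied". It defines no seroconversion date and does not say whether the cut is by study day or by analysis visit.

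SAP 4.2.3.4.1, the section it borrows from, concerns RT-PCR-positive symptomatic illness, where the event date is normally symptom onset. It handles the cut-off day in two ways:

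- An event that "occurs on or after Day 183, or Day 365, the participant will be considered as not having an event, respectively". This excludes the cut-off day itself.
- The follow-up rule censors "When the minimum of the date of censoring and date of Day 183 or Day 365 is prior to date of event". An event exactly on Day 183 or Day 365 is then not censored and counts.

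Protocol 1.3, Tables 1 and 2, schedules the blood sample (row "Serum sample for SARS-CoV-2 serology (anti-nucleocapsid) testing (predose on days of IMP administration") on Days 1, 29, 92, 183, 212, 274, 365 and 456 in both arms, and also on Day 121 in Arm A only. The window at Day 183 and Day 365 is ±7 days. Protocol Table 3 adds one sample at the Early Discontinuation visit and none at the Month 18, 21 or 24 contacts. The illness-visit schedule (Protocol Table 4) has no anti-nucleocapsid sample.

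The SAP has its own visit convention for this assay, in "Table 3: Analysis windows for serum sample for SARS-CoV-2 serology, ADA and SARS-CoV-2 nAbs levels". The Day 183 visit runs to Day 197 and the Day 365 visit to Day 410, with the same upper limits in both arms.

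**The concern.** A cut at a calendar day suits an event with its own onset date. Here the only date available is that of the blood draw, and both cut-offs coincide with the nominal day of a draw. A positive sample on Day 183 reflects infection since the previous sample, that is, during the period a 6-month rate is meant to describe. A strict reading of *before* puts it outside that period.

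Two things follow. Both timed rates stop short of their labels for participants who attend on time or late. At Day 183 the shortfall is also unequal, because only Arm A has a Day 121 draw to fall back on.

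Protocol 8.5.2.2 makes seroconversion the measure of the SARS-CoV-2 infection rate, the results are shown by arm, and SAP 4.2.3.5 plans no sensitivity analysis. A reader comparing the 6-month rates could take a sampling artefact for a difference between regimens.

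**Working it through.** **Plan's own figures.** The documents give no infection or seroconversion rate. Their only stated probability is in the sample-size section: at least one AE in 100 participants at a true rate of 3%, 1 − 0.97^100 = 0.952, which matches the stated 95%. It does not bear on this endpoint.

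**Inputs from the documents.** Draw days and ±7-day windows from Protocol Tables 1 and 2; cut-offs from SAP 4.2.3.4.2.

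**Assumptions not in the documents.** The hazard of infection is constant and equal in the arms; there is no seroconversion lag and no censoring; earlier draws are on their nominal day. The risk by Day 183 is taken as 10%, with a range of 5% to 30%.

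**Step 1: last draw strictly before each cut-off.**

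| Cut-off | Arm A | Arm B |
|---|---|---|
| Day 183 | Day 121 | Day 92 |
| Day 365 | Day 274 | Day 274 |

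The 29-day arm gap exists at Day 183 only.

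**Step 2: share of the period covered if the cut-off sample is lost for everyone.** This applies if the cut is by visit label, or if every draw is on or after the nominal day.

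- Day 183, Arm A: (121 − 1)/182 = 66%. Arm B: (92 − 1)/182 = 50%.
- Day 365, both arms: (274 − 1)/364 = 75%.

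**Step 3: study-day reading, attendance uniform over ±7 days.** Draws on Days 176–182 count (7 of 15 days) and draws on Days 183–190 do not (8 of 15). The days 176 to 182 sum to 7 × 179 = 1253.

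- Mean effective end, Arm A: (1253 + 8 × 121)/15 = Day 148.1; coverage 147.1/182 = 81%.
- Arm B: (1253 + 8 × 92)/15 = Day 132.6; coverage 131.6/182 = 72%.
- Day 365, both arms, where Days 358–364 count: (7 × 361 + 8 × 274)/15 = Day 314.6; coverage 313.6/364 = 86%.

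If a draw exactly on the cut-off day counts, as the follow-up rule implies, 8 of 15 days count and the mean ends at the Day 183 cut become Day 152.2 (A) and Day 138.7 (B).

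**Step 4: expected seroconverters per 100 baseline-negative participants.** With λ = −ln(1 − 0.10)/182, the expected count by day d is 100 × (1 − exp(−λ(d − 1))).

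| Case (10% risk by Day 183) | Arm A | Arm B | Ratio | Difference |
|---|---|---|---|---|
| Day 183 cut, sample lost for all | 6.71 | 5.13 | 1.31 | 1.58 |
| Day 183 cut, uniform ±7 days | 8.15 | 7.31 | 1.12 | 0.84 |
| Day 183 visit included | 10.0 | 10.0 | 1.00 | 0 |
| Day 365 cut, sample lost for all | 14.6 | 14.6 | 1.00 | 0 |
| Day 365 cut, uniform ±7 days | 16.6 | 16.6 | 1.00 | 0 |
| Day 365 visit included | 19.0 | 19.0 | 1.00 | 0 |

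Over assumed risks of 5% to 30%, the Day 183 ratio is 1.31 to 1.28 with the sample lost for all, and 1.12 to 1.11 with uniform attendance.

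**Step 5: scale.** With 100 evaluable participants per arm, the standard error of the difference in the first row is √(0.0671 × 0.9329/100 + 0.0513 × 0.9487/100) = 0.033, or 3.3 percentage points. The artefact is 1.6 points at most at this risk.

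**The case against.** Much of the opposing case stands and limits the point.

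- **Not every cut-off sample is lost.** A reader might infer that all Day 183 and Day 365 samples are discarded. On a study-day reading, in-window draws on Days 176–182 and 358–364 count, and every sample stays in the overall rate.
- **The arms are not cut differently throughout.** A reader might extend the arm gap to the 12-month rate. The schedules are identical from Day 183 onward and both arms fall back to Day 274.
- **The strict rule is partly inferred.** The sentence excluding events on or after the cut-off is written for RT-PCR-positive illness. Section 4.2.3.4.2 imports only the censoring criteria, and the follow-up rule disagrees about the cut-off day. However, the word *before* in 4.2.3.4.2 already excludes on-time samples.
- **The two scenarios should not be mixed.** The 1.3 ratio needs the Day 183 sample to be lost for everyone. Dependence on attending a few days early or late belongs to the study-day reading, where the ratio is about 1.1.
- **Early termination is not shown to make this worse overall.** After a last dose on Day 183, participants attend Day 274, "followed by an Early Discontinuation visit in place of the Day 365 visit", at least 6 months after that dose. That may push samples past the cut-off. But an on-time Day 365 sample is already excluded, and participants last dosed on Day 274 keep a Day 365 visit. The documents give no counts.
- **Understated relative to what?** If the target is responses observed before a calendar day, the rate is correct by definition. It is low only as a measure of infections acquired through Day 183 or Day 365. For a by-arm 6-month rate, that is the natural reading.

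The artefact is also small beside sampling error. Unlike sampling error, though, it has a fixed direction and can be removed.

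**Conclusion.** The point holds in limited form. The timed seroconversion rates are cut on the nominal day of a draw, so a literal reading excludes on-time and late samples that report on the period in question.

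At Day 183 this makes Arm A look about 1.1 to 1.3 times as high as Arm B under equal risk, or about 0.8 to 1.6 per 100 at an assumed 10% risk. At Day 365 the rate is understated in both arms alike: about 75% coverage if the sample is lost for all and about 86% with uniform attendance. These sizes rest on a constant equal hazard, no seroconversion lag and no censoring. Any further loss from early termination is possible but cannot be sized.

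The endpoint is exploratory and no hypothesis is tested, so what is affected is interpretation of the by-arm 6- and 12-month rates. The overall rate and the study's primary conclusions are not touched. The SAP should be changed because the correction is cheap and the artefact falls on a comparison that will be displayed.

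**What to change.** In SAP 4.2.3.4.2:

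1. Define the seroconversion date as the collection date of the first positive sample.
2. Replace the wording that cuts before Day 183 or Day 365 with: up to and including the Day 183 (or Day 365) analysis visit, as windowed in SAP Table 3.
3. State that any positive sample in those windows counts. Otherwise the rule in SAP 3.3.2 that keeps only the result closest to the expected date could drop a positive.
4. State that, for this endpoint, follow-up ends at that visit's sample and not at Day 183 or Day 365; otherwise a positive on Days 184–197 would fall after follow-up has ended. Leave the other censoring reasons as they are.

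In SAP 4.2.3.4.1, reconcile the two statements about an event exactly on the cut-off day.

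There is a downside. The Table 3 upper limits admit infections up to 197 − 183 = 14 days and 410 − 365 = 45 days after the nominal day. They are the same in both arms, but attendance within them may differ. Either report the distribution of sample days by arm, or use the protocol's ±7-day window as the upper limit (Days 190 and 372).

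The cost is a few sentences of SAP text and changed date conditions in the seroconversion table. No new data are needed.
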